9.1.1 CAEPRs for CB-5339 (NSC 814100)

The Comprehensive Adverse Events and Potential Risks list (CAEPR) provides a single list of reported and/or potential adverse events (AE) associated with an agent using a uniform presentation of events by body system. In addition to the comprehensive list, a subset, the Specific Protocol Exceptions to Expedited Reporting (SPEER), appears in a separate column and is identified with bold and italicized text. This subset of AEs (SPEER) is a list of events that are protocol specific exceptions to expedited reporting to NCI (except as noted below). Refer to the 'CTEP, NCI Guidelines: Adverse Event Reporting Requirements' http://ctep.cancer.gov/protocolDevelopment/electronic_applications/docs/aeguidelines.pdf for further clarification. The CAEPR does not provide frequency data; refer to the Investigator's Brochure for this information. Below is the CAEPR for CB-5339 tosylate.

NOTE: Report AEs on the SPEER **ONLY IF** they exceed the grade noted in parentheses next to the AE in the SPEER. If this CAEPR is part of a combination protocol using multiple investigational agents and has an AE listed on different SPEERs, use the lower of the grades to determine if expedited reporting is required.

Version 1.0, June 20, 2019

Adverse Events with Possible Relationship to CB-5339 tosylate (CTCAE 5.0 Term)	Specific Protocol Exceptions to Expedited Reporting (SPEER)
BLOOD AND LYMPHATIC SYSTEM DISORDERS	
Anemia ²	
EYE DISORDERS	
Eye disorders - Other (chromatopsia) ²	
Eye disorders - Other (dyschromatopsia) ²	
Eye disorders - Other (intermittent visual loss) ²	
Eye disorders - Other (photopsia) ²	
Photophobia ²	
Vision decreased ²	
GASTROINTESTINAL DISORDERS	
Constipation ²	
Diarrhea ²	
Nausea ²	
Vomiting ²	
GENERAL DISORDERS AND ADMINISTRATION SITE DISORDERS	
Edema limbs ²	
Fatigue ²	
INVESTIGATIONS	
Alanine aminotransferase increased ²	

METABOLIC AND NUTRITION DISORDERS	
Hypercalcemia ²	
Hypokalemia ²	
MUSCULOSKELETAL AND CONNECTIVE TISSUE DISORDERS	
Back pain ²	
Muscle cramp ²	
RENAL AND URINARY SYSTEM DISORDERS	
Acute kidney injury ²	

¹ This table will be updated as the toxicity profile of the agent is revised. Updates will be distributed to all Principal Investigators at the time of revision. The current version can be obtained by contacting mailto:[contact]. Your name, the name of the investigator, the protocol and the agent should be included in the e-mail.

² All adverse events listed in the CAEPR table were from phase1 clinical toxicity data obtained from patients treated with a similar p97 inhibitor CB-5083. In nonclinical species, CB-5083 caused changes in electroretinography but CB-5339 did not. Additionally, CB-5339 is designed to be less potent on phospho-diesterase E6, the off-target enzyme which mediates eye adverse events.

Animal Data: The following toxicities have been observed in animal studies with CB-5339 tosylate:

Dogs

GENERAL DISORDERS AND ADMINISTRATION SITE CONDITIONS - Moribund condition - female beagle dogs

INVESTIGATIONS - Increased cholesterol; Weight loss

METABOLISM AND NUTRITION DISORDERS - Dehydration; Reduced food consumption

Rats

BLOOD AND LYMPHATIC SYSTEM DISORDERS - Lower Mean Corpuscular Hemoglobin Concentration (MCHC) - male rats; Lymphoid depletion/necrosis; Marrow hypocellularity; Slight lymphoid depletion/necrosis in thymus - female rats

GASTROINTESTINAL DISORDERS - Moderate glandular stomach mucosal atrophy - female rat; Pancreas acinar atrophy

INVESTIGATIONS - Low reticulocyte count; Low triglyceride concentration - male rats; Minimally higher ALT

Note: CB-5339 tosylate in combination with other agents could cause an exacerbation of any adverse event currently known to be caused by the other agent, or the combination may result in events never previously associated with either agent.

9.2 Adverse Event Characteristics

- **CTCAE term (AE description) and grade:** The descriptions and grading scales found in the revised NCI Common Terminology Criteria for Adverse Events (CTCAE) version 5.0 will be utilized for AE reporting. All appropriate treatment areas should have access to a copy of the CTCAE version 5.0. A copy of the CTCAE version 5.0 can be downloaded from the CTEP website http://ctep.cancer.gov/protocolDevelopment/electronic_applications/ctc.htm.
- **For expedited reporting purposes only:**
 - AEs for the agent that are ***bold and italicized*** in the CAEPR (i.e., those listed in the SPEER column, Section 10.1) should be reported through CTEP-AERS only if the grade is above the grade provided in the SPEER.
 - Other AEs for the protocol that do not require expedited reporting are outlined in Section 9.3.4.
- **Attribution of the AE:**
 - Definite – The AE is *clearly related* to the study treatment.
 - Probable – The AE is *likely related* to the study treatment.
 - Possible – The AE *may be related* to the study treatment.
 - Unlikely – The AE is *doubtfully related* to the study treatment.
 - Unrelated – The AE is *clearly NOT related* to the study treatment.

9.3 Expedited Adverse Event Reporting

9.3.1 Rave-CTEP-AERS Integration

The Rave Cancer Therapy Evaluation Program Adverse Event Reporting System (CTEP-AERS) integration enables evaluation of post-baseline AEs entered in Rave to determine whether they require expedited reporting, and facilitates entry in CTEP-AERS for those AEs requiring expedited reporting.

All AEs that occur after baseline are collected in Medidata Rave using the Adverse Event form, which is available for entry at each treatment or reporting period, and used to collect AEs that start during the period or persist from the previous reporting period. CRA will enter AEs that occur prior to the start of treatment on a baseline form that is not included in the Rave-CTEP-AERS integration. AEs that occur prior to enrollment must begin and end on the baseline Adverse Event form and should not be included on the standard Adverse Events form that is available at treatment unless there has been an increase in grade.

Prior to sending AEs through the rules evaluation process, site staff should verify the following on the Adverse Event form in Rave:

- The reporting period (course/cycle) is correct, and
- AEs are recorded and complete (no missing fields) and the form is query-free.

The CRA reports AEs in Rave at the time the Investigator learns of the event. If the CRA modifies an AE, it must be re-submitted for rules evaluation.

Upon completion of AE entry in Medidata Rave, the CRA submits the AE for rules evaluation by completing the Expedited Reporting Evaluation form. Both NCI and protocol-specific reporting rules evaluate the AEs submitted for expedited reporting. A report is initiated in CTEP-AERS using information entered in Medidata Rave for AEs that meet reporting requirements. The CRA completes the report by accessing CTEP-AERS via a direct link on the Medidata Rave Expedited Reporting Evaluation form.

In the rare occurrence that Internet connectivity is lost, a 24-hour notification is to be made to CTEP by telephone at [contact]. Once internet connectivity is restored, the 24-hour notification that was phoned in must be entered immediately into CTEP-AERS using the direct link from Medidata Rave.

Additional information about the CTEP-AERS integration is available on the CTSU website:

- Study specific documents: Protocols > Documents > Education and Promotion, and
- Expedited Safety Reporting Rules Evaluation user guide: Resources > CTSU Operations Information > User Guides & Help Topics.

NCI requirements for SAE reporting are available on the CTEP website:

- NCI Guidelines for Investigators: Adverse Event Reporting Requirements is available at
https://ctep.cancer.gov/protocolDevelopment/electronic_applications/docs/aeguidelines.pdf.

9.3.2 Distribution of Adverse Event Reports

CTEP-AERS is programmed for automatic electronic distribution of reports to the following individuals: Principal Investigator and Adverse Event Coordinator(s) (if applicable) of the Corresponding Organization or Lead Organization, the local treating physician, and the Reporter and Submitter. CTEP-AERS provides a copy feature for other e-mail recipients.

9.3.3 Expedited Reporting Guidelines

Use the NCI protocol number and the protocol-specific patient ID assigned during trial registration on all reports.

Note: A death on study requires both routine and expedited reporting, regardless of causality. Attribution to treatment or other cause must be provided.

Death due to progressive disease should be reported as **Grade 5 “Disease progression”** in the system organ class (SOC) “General disorders and administration site conditions.” Evidence that the death was a manifestation of underlying disease (e.g., radiological changes suggesting tumor growth or progression; clinical deterioration associated with a disease process) should be submitted.

Phase 1 and Early Phase 2 Studies: Expedited Reporting Requirements for Adverse Events that Occur on Studies under an IND/IDE within 30 Days of the Last Administration of the Investigational Agent/Intervention ^{1, 2}

FDA REPORTING REQUIREMENTS FOR SERIOUS ADVERSE EVENTS (21 CFR Part 312)

NOTE: Investigators **MUST** immediately report to the sponsor (NCI) **ANY** Serious Adverse Events, whether or not they are considered related to the investigational agent(s)/intervention (21 CFR 312.64)

An adverse event is considered serious if it results in **ANY** of the following outcomes:

- 1) Death
- 2) A life-threatening adverse event
- 3) An adverse event that results in inpatient hospitalization or prolongation of existing hospitalization for \geq 24 hours
- 4) A persistent or significant incapacity or substantial disruption of the ability to conduct normal life functions
- 5) A congenital anomaly/birth defect.
- 6) Important Medical Events (IME) that may not result in death, be life threatening, or require hospitalization may be considered serious when, based upon medical judgment, they may jeopardize the patient or subject and may require medical or surgical intervention to prevent one of the outcomes listed in this definition. (FDA, 21 CFR 312.32; ICH E2A and ICH E6).

ALL SERIOUS adverse events that meet the above criteria **MUST** be immediately reported to the NCI via electronic submission within the timeframes detailed in the table below.

Hospitalization	Grade 1 and Grade 2 Timeframes	Grade 3-5 Timeframes
Resulting in Hospitalization \geq 24 hrs	10 Calendar Days	24-Hour 5 Calendar Days
Not resulting in Hospitalization \geq 24 hrs	Not required	

NOTE: Protocol specific exceptions to expedited reporting of serious adverse events are found in the Specific Protocol Exceptions to Expedited Reporting (SPEER) portion of the CAEPR.

Expedited AE reporting timelines are defined as:

- o “24-Hour; 5 Calendar Days” - The AE must initially be submitted electronically within 24 hours of learning of the AE, followed by a complete expedited report within 5 calendar days of the initial 24-hour report.
- o “10 Calendar Days” - A complete expedited report on the AE must be submitted electronically within 10 calendar days of learning of the AE.

¹Serious adverse events that occur more than 30 days after the last administration of investigational agent/intervention and have an attribution of possible, probable, or definite require reporting as follows:

Expedited 24-hour notification followed by complete report within 5 calendar days for:

- All Grade 3, 4, and Grade 5 AEs

Expedited 10 calendar day reports for:

- Grade 2 AEs resulting in hospitalization or prolongation of hospitalization

²For studies using PET or SPECT IND agents, the AE reporting period is limited to 10 radioactive half-lives, rounded UP to the nearest whole day, after the agent/intervention was last administered. Footnote “1” above applies after this reporting period. Effective Date: May 5, 2011

9.3.4 Additional Protocol-Specific Expedited Adverse Event Reporting Exclusions

None.

9.4 Routine Adverse Event Reporting

All Adverse Events **must** be reported in routine study data submissions. **AEs reported expeditiously through CTEP-AERS must also be reported in routine study data submissions.**

Adverse event data collection and reporting, which are required as part of every clinical trial, are done to ensure the safety of patients enrolled in the studies as well as those who will enroll in future studies using similar agents. AEs are reported in a routine manner at scheduled times during the trial using Medidata Rave. For this trial the Adverse Event CRF is used for routine AE reporting in Rave.

9.5 Pregnancy

Although not an adverse event in and of itself, pregnancy as well as its outcome must be documented via **CTEP-AERS**. In addition, the **Pregnancy Information Form** included within the NCI Guidelines for Adverse Event Reporting Requirements must be completed and submitted to CTEP. Any pregnancy occurring in a patient or patient's partner from the time of consent to 90 days after the last dose of study drug must be reported and then followed for outcome. Newborn infants should be followed until 30 days old. Please see the "NCI Guidelines for Investigators: Adverse Event Reporting Requirements for DCTD (CTEP and CIP) and DCP INDs and IDEs" (at http://ctep.cancer.gov/protocolDevelopment/adverse_effects.htm) for more details on how to report pregnancy and its outcome to CTEP.

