$\geq 60 \text{ mL/min}/1.73 \text{ m}^2$ for patients with creatinine levels above 1.5X institutional normal
- 3.1.7 The effects of CB-5339 on the developing human fetus are unknown. For this reason and because p97 inhibitors agents may be teratogenic, women of child-bearing potential and men must agree to use adequate contraception (hormonal or barrier method of birth control; abstinence) prior to study entry and for the duration of study participation and for

4 months afterwards. Should a woman become pregnant or suspect she is pregnant while she or her partner is participating in this study, she should inform her treating physician immediately. Men treated or enrolled on this protocol must also agree to use adequate contraception prior to the study, for the duration of study participation, and 4 months after completion of CB-5339 administration.

- 3.1.8 Ability to understand and the willingness to sign a written informed consent document.
- 3.1.9 Subjects on the expansion cohort must also be willing to undergo two core biopsy procedures and have a lesion amenable to biopsy.
- 3.1.10 Left ventricular ejection fraction \geq the lower limit of normal by ECHO at entry.
- 3.1.11 Mean QT interval corrected for heart rate (QTc) <470 ms using Fridericia's Correction.

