Route of administration: oral; capsules should be taken on an empty stomach (i.e., either 1 hour before or 2 hours after meals) with water.

Potential Drug Interactions: *In vitro* studies suggest CB-5339 tosylate is hepatically metabolized, with metabolic pathways not fully defined.

In vitro, CB-5339 tosylate showed moderate inhibition of CYP2C9 and CYP2C19, and weak inhibition of CYP1A2 and CYP2D6. CB-5339 tosylate did not inhibit CYP3A4. Use caution when co-administered with CYP2C9 and CYP2C19 substrates.

In vitro, CB-5339 tosylate is > 98% protein-bound in human plasma. Use caution when co-administered with other medications that are highly protein-bound.

Patient Care Implications: CB-5339 tosylate must not be administered to pregnant or nursing females. Women study participants of reproductive potential and fertile men study participants and their partners must abstain or use effective contraception while receiving study treatment and for at least 4 months after the last dose.

Availability: CB-5339 is an investigational agent supplied to investigators by the Division of Cancer Treatment and Diagnosis (DCTD), NCI. CB-5339 is provided to the NCI under a Collaborative Agreement between the Pharmaceutical Collaborator and the DCTD, NCI (see Section 12.3).

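### Mandatory pregnancy reporting (section 9.5) ends at 90 days after the last dose, about a month before the 4-month contraception window in sections 3.1.7 and 6.1, so pregnancies starting late in that window need not be reported

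*Combined protocol and SAP*

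**What the plan says.** Three operative sections bear on this point.

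- **Section 9.5 (Pregnancy)** sets the reporting duty. A pregnancy in a patient or a patient's partner "from the time of consent to 90 days after the last dose of study drug must be reported", and its outcome is then followed. Newborns are followed to 30 days of age. For details of how to report, the section refers to an NCI guideline.
- **Section 6.1 (Patient Care Implications)** sets a contraception duty. Women of reproductive potential, fertile men and their partners "must abstain or use effective contraception while receiving study treatment and for at least 4 months after the last dose".
- **Section 3.1.7 (Eligibility Criteria)** sets the same duty and gives the reason: "because p97 inhibitors agents may be teratogenic, women of child-bearing potential and men must agree to use adequate contraception". Its general sentence runs the duty through study participation and 4 months beyond. A further sentence, on men, runs it "for the duration of study participation, and 4 months after completion of CB-5339 administration".

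Two other places determine whether a late pregnancy would come to light. Section 3.1.7 covers a woman who becomes or suspects she is pregnant "while she or her partner is participating in this study, she should inform her treating physician immediately". Section 5.6 sets follow-up at 30 days after the last dose, with one phone call between Days 27 and 30. It ends earlier if the patient joins another protocol or receives standard of care, and continues only for unresolved toxicity of Grade 2 or higher.

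**The concern.** The protocol asks participants to avoid conception for 4 months after treatment because the drug may harm a fetus, but it obliges sites to report and follow pregnancies for only the first 90 days. It gives no reason for the shorter reporting period.

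This is a first-in-human trial, and section 3.1.7 states that effects on the developing fetus are unknown. Section 13 goes further and calls teratogenic effects of p97 inhibitors likely. Any pregnancy within the period the protocol treats as needing protection is therefore informative, including one with a normal outcome: without normal outcomes, a reported harm has no denominator. At stake is the completeness of fetal-exposure safety data. Dose-limiting toxicity assessment, the recommended phase 2 dose, and the pharmacokinetic, pharmacodynamic and response analyses are not affected.

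**Working it through.** The plan states no figure for this gap, so there is none to reproduce. The check compares two windows.

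**Inputs**

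| Quantity | Value | Source |
|---|---|---|
| End of mandatory pregnancy reporting | 90 days after last dose | 9.5 |
| End of contraception, women, fertile men and partners | at least 4 months after last dose | 6.1 |
| End of contraception, men | 4 months after completion of CB-5339 | 3.1.7 |
| End of contraception, women | 4 months after study participation | 3.1.7 |
| Scheduled follow-up | 30 days after last dose | 5.6 |

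**Step 1: convert 4 months to days.** In a non-leap year, four consecutive calendar months total between 120 days (for example January to April: 31 + 28 + 31 + 30) and 123 days (for example May to August: 31 + 30 + 31 + 31).

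**Step 2: gap counted from the last dose (6.1, and 3.1.7 for men).** Gap = contraception window − reporting window.

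- Lower: 120 − 90 = 30 days.
- Upper: 123 − 90 = 33 days.

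**Step 3: gap counted from the end of participation (3.1.7 for women).** The protocol does not say whether participation includes the 30-day follow-up. Assuming that it does, and that follow-up runs its full length:

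- Window = 30 + 120 = 150 days to 30 + 123 = 153 days after the last dose.
- Gap = 150 − 90 = 60 days to 153 − 90 = 63 days.

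If participation ends with the last dose, the result is that of step 2.

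**Step 4: does any reading close the gap?** Assuming that a month means a 28-day cycle gives 4 × 28 = 112 days and a gap of 112 − 90 = 22 days. The gap shrinks but remains.

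**Step 5: does another reporting route cover the interval?** Section 9.3.3 lists a congenital anomaly or birth defect as a serious event. Its first footnote keeps expedited reporting open beyond 30 days after the last dose for serious events attributed as possible, probable or definite: all of Grade 3 to 5, and those of Grade 2 that result in or prolong hospitalization. A related birth defect could come through this route. The pregnancy itself would not, because 9.5 says that pregnancy is not in itself an adverse event. Nor would a normal outcome, or a harm judged unrelated.

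**Step 6: would a late pregnancy be detected?** The last scheduled contact is at about day 30. From then to day 90 is 60 days in which reporting is mandatory but no contact is planned, apart from patients followed for toxicity. The 3.1.7 instruction to inform the physician is tied to participation. Lengthening the period in 9.5 alone would therefore add a duty without a way of finding cases.

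**The case against.** The strongest reply is that the sections do not contradict one another. Contraception is a duty of the participant and pregnancy reporting a duty of the site, and they need not have equal length. The protocol nowhere defines a single period of reproductive risk, and 4 months can be read as a precaution. This stands as far as it goes: the mismatch is a design choice without a stated reason, not a logical error. It does not explain why the outcome of a pregnancy in the last part of a protective window should be of no interest.

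A reader might infer that pregnancies in the fourth month go unreported. The documents do not support that. Section 9.5 only stops requiring the report. A site may still report, the late serious adverse event rule covers a serious, at least possibly related birth defect, and the NCI guideline cited in 9.5 may set a wider duty. That guideline and the consent form were not available to check. Section 9.5 does, however, state the reporting period itself and cites the guideline for how to report.

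A reader might also take one gap of about 30 days to apply to every patient and partner. That is too broad. The duty concerns women of child-bearing potential, fertile men and their partners, and 3.1.7 ties the women's window to participation and not to the last dose. The change of anchor can lengthen the gap but does not remove it. Likewise, 30/120 = 25% describes only the post-treatment part of a window that starts before study entry, so the gap is a smaller share of the whole period of required contraception.

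Finally, few pregnancies are to be expected with an accrual ceiling of 40 patients with advanced cancer. This is correct, and it limits the importance of the point.

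**Conclusion.** The point holds as a minor one. Mandatory reporting and outcome follow-up under 9.5 end 30 to 33 days before the contraception window in 6.1, and before the men's window in 3.1.7. For women under 3.1.7 the gap is 60 to 63 days if participation includes a full 30-day follow-up. A pregnancy starting in that interval need not be reported under 9.5.

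The figures assume calendar months; 28-day months give 22 days. The conclusion assumes that neither the cited NCI guideline nor the consent form imposes a longer reporting period. The number of pregnancies affected cannot be estimated from the documents and is likely to be small.

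**What to change.** - Reconcile sections 3.1.7, 6.1 and 9.5 so that the 9.5 reporting period covers at least the full contraception window that the protocol states, counted from the same anchor (last dose or end of participation). How long contraception should last is a clinical matter and is not addressed here.
- Keep the existing text in 9.5 on outcome and newborn follow-up.
- Extend the instruction in 3.1.7 to inform the physician of a pregnancy to the same period, for patients and partners, because scheduled contact ends at about day 30.

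The cost is a short edit to 9.5 and one to 3.1.7, with any patient-facing text brought into line. Extra reporting would be negligible, and no visit, dose or analysis changes.
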